15.1.2 Adverse Events Leading to Treatment Discontinuation

TEAEs leading to permanent discontinuation of trial treatment will be summarized by treatment and overall including number of subjects, percentage and number of events.

A listing of TEAEs leading to permanent discontinuation of a trial treatment will additionally be provided.

15.2 Deaths, Other Serious Adverse Events, and Other Significant Adverse Events

15.2.1 Deaths

All deaths as well as reason for death will be based on information from the “Report of Subject Death” eCRFs.

Listing of deaths, if any, will be provided displaying date and cause of death (including TEAE leading to death and relatedness to trial treatment, when applicable), and date and time of treatment administration.

15.2.2 Serious Adverse Events

A summary table of SAEs, if any, by treatment and overall will be provided displaying the number and percentage of subjects by treatment with at least one SAE and the number of SAE overall and by system organ class and preferred term. Group/SOC terms and PTs within each group/SOC term will be sorted alphabetically.

Listing of SAEs, if any, will be provided in addition.

15.2.3 Other Significant Adverse Event

15.2.3.1 Adverse Events of Special Interest

Healthy subjects might experience asymptomatic elevations in serum lipase and amylase. Any elevation in serum lipase and amylase of Grade ≥ 3 will lead to the recording of an adverse event of special interest (AESI). The severity of these AEs should be defined based on clinical judgment of the Investigator and defined according to NCI-CTCAE Severity Scale.

Adverse events of special interest will be presented in a separate data listing.

15.3 Clinical Laboratory Evaluation

All laboratory data will be reported with SI units. Laboratory parameters will be listed by subject and time-point and summarized indicating the treatment at the respective time-point using descriptive statistics for absolute values and change from baseline over time. Data listings of abnormalities as per the NCI-CTCAE guideline will be provided. Shift tables for laboratory tests will be presented by treatment. Shift tables will be based on NCI-CTCAE grades, where possible, and on normal ranges otherwise. They will be produced for

- End of Trial versus Screening
- Discharge versus Pre-dose (Tepotinib administration) within periods.

Laboratory values that are outside the normal range will also be flagged in the data listings, along with corresponding normal ranges and NCI-CTCAE grade and will additionally be listed separately.

See section 7.4.3 of the clinical study protocol for a table of the safety laboratory evaluations.

Safety laboratory values are separated into:

- Hematology (including coagulation)
- Biochemistry
- Urinalysis
- Other tests

Tables will be produced for the groups hematology (including coagulation), and biochemistry.

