- f Day 4 measurements (72 h measurements) may be performed (within 60 min, PK sampling within 30 min) prior to tepotinib dosing on Day 1 of Period 2.
- g Coagulation parameters will be determined pre-dose and 4 h post-dose on Day 1 and 24 h post-dose on Day 2.
- h PGx blood samples of 2 x 2 mL (optional) to be drawn at pre-dose Day 1.
- i Only to be performed in case of a prolonged interval of more than 7 days between Period 1 (Day 4) and Period 2 (Day 1)

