On Day 8, a standardized breakfast will be administered 30 min prior to tepotinib and dabigatran etexilate administration and must be consumed completely within 25 min. 30 min after start of the breakfast, 500 mg tepotinib and 75 mg dabigatran etexilate will be taken together with 240 mL of water.
- g PK blood samples for determination of tepotinib and its metabolites will be collected on Day 6 at pre-dose (within 60 min prior to administration), on Day 7 at pre-dose (within 60 min prior to administration) and 15, 30, 45, 60, 90 min, and 2, 3, 4, 6, 8, 12 and 24 h post-dose prior to dosing on Day 8 (within 60 min prior to administration).
- h PK blood samples for determination of total dabigatran will be collected at pre-dose (within 60 min prior to administration) and 15, 30, 45, 60, 90 min, and 2, 3, 4, 6, 8, 12, 24, 36, 48 and 72 h post-dose.
- i Coagulation parameters: Pre-dose on Day 1, pre-dose and 4 h post-dose on Day 8, and 24 h after the last dose on Day 9.
- j Discharge after completion of all 72 h post-dose activities.

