### **Period 1: Dabigatran Etexilate alone**

#### **Day -1 (admission)**

Subjects will be hospitalized from the morning of Day -1 until completion of the 72 h assessments in the morning of Day 11 of Period 2.

On admission on Day -1 the following will be done:

- Physical examination
- Vital signs
- 12-lead ECG
- Blood and urine samples for safety laboratory assessments (including drugs of abuse and a urine pregnancy test in females)
- Alcohol breath test
- Prior medication and concomitant medication
- AEs
- Evaluation of inclusion and exclusion criteria.

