**Coagulation**

c Period 1: pre-dose and 4 h post-dose on Day 1 and 24 h post-dose on Day 2 = 3 samples

d Period 2: pre-dose on Day 1, pre-dose and 4 h post-dose on Day 8 and 24 h after the last dose on Day 9 = 4 samples

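### Neither shift contrast in SAP 15.3 can show a coagulation change after dabigatran: none of the 4 post-dabigatran samples per subject enters a shift table

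*SAP*

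**What the plan says.** SAP 15.3 covers coagulation explicitly: "Tables will be produced for the groups hematology (including coagulation), and biochemistry". The parameters are thrombin time, aPTT and the Hemoclot thrombin inhibitor assay (Protocol Table 3). The same section says "Shift tables for laboratory tests will be presented by treatment" and names two contrasts: End of Trial against Screening, and "Discharge versus Pre-dose (Tepotinib administration) within periods". SAP 9 gives two treatment labels, dabigatran and dabigatran + tepotinib. It defines baseline, period by period, as the last scheduled value before the first drug of that period.

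The coagulation schedule is in the protocol:

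- Period 1 (Table 1, footnote g): "Coagulation parameters will be determined pre-dose and 4 h post-dose on Day 1 and 24 h post-dose on Day 2".
- Period 2 (Table 2, footnote i): "Coagulation parameters: Pre-dose on Day 1, pre-dose and 4 h post-dose on Day 8, and 24 h after the last dose on Day 9". Appendix II confirms the count: "24 h after the last dose on Day 9 = 4 samples".
- One further sample at Screening and one at End of Trial.

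On discharge, Table 2, footnote j reads "Discharge after completion of all 72 h post-dose activities". Protocol 7.1.2 keeps subjects in the unit "until completion of the 72 h assessments in the morning of Day 11 of Period 2".

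Protocol 8.5.4 says laboratory parameters will be summarised by shifts after dosing relative to baseline. SAP 7 states that the protocol's methods were adopted and declares only a change to the scatter plots.

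**The concern.** A shift table needs a value at both of its time points. For coagulation, the discharge contrast has no discharge value. The other contrast has both values, but one precedes all drug and the other comes about a week after the last dose, so it cannot show an effect of either treatment. It also spans both periods and so fits neither treatment label, although the tables are to be split by treatment.

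This matters because stronger anticoagulation is the direct safety consequence of the interaction under study. Changes in safety laboratory values are a secondary endpoint (Protocol 8.3.2), and Protocol 5.2.3 gives the possible prolongation of thrombin time and aPTT as the reason for measuring them. Missing from the planned output is a by-treatment count of subjects who move out of range after dabigatran. A reader would have to build it from the listings.

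**Working it through.** The point is structural, so the check is a count of time points followed by a test of each contrast against the schedule.

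**1. Reproduce the plan's count.** Appendix II: Screening 1 + Period 1 3 + Period 2 4 + End of Trial 1 = 9 coagulation samples per subject, and 9 × 3.0 mL = 27.0 mL. Both agree with the table. The footnotes of Tables 1 and 2 give the same nine time points.

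**2. Place each sample in the two contrasts.**

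| Coagulation sample | 4 h or 24 h after dabigatran | Discharge vs tepotinib pre-dose | End of Trial vs Screening |
|---|---|---|---|
| Screening | no | no | yes |
| Period 1 Day 1 pre-dose | no | no | no |
| Period 1 Day 1, 4 h | yes | no | no |
| Period 1 Day 2, 24 h | yes | no | no |
| Period 2 Day 1 pre-dose | no | reference only, no partner | no |
| Period 2 Day 8 pre-dose | no | no | no |
| Period 2 Day 8, 4 h | yes | no | no |
| Period 2 Day 9, 24 h | yes | no | no |
| End of Trial | no | no | yes |

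*Discharge contrast.* Period 2 has a tepotinib pre-dose value but no Day 11 value: 0 pairs. Period 1 has no tepotinib dose and no planned discharge: 0 pairs. The optional Day 4 checks after a prolonged interval cover hematology, biochemistry and urinalysis, not coagulation (Table 1). For hematology and biochemistry the contrast does work in Period 2, since both are drawn on Day 1 pre-dose and on Day 11.

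*End of Trial contrast.* One pair per subject, using 2 of 9 samples and 0 of the 4 post-dabigatran samples.

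**3. Is End of Trial off drug?** The visit is 7 ± 1 days after the last dose, that is 144 to 192 h. Fraction left = 0.5^(time / half-life).

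- Dabigatran, half-life 8.4 h: 144/8.4 = 17.1 to 192/8.4 = 22.9 half-lives, so effectively none.
- Tepotinib, half-life about 30 h: 144/30 = 4.8 to 192/30 = 6.4 half-lives, or 3.6% down to 1.2% left. Protocol 5.2.2 treats this as full elimination.

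**4. Is the SAP 9 baseline usable in Period 2?** It is drawn before the first tepotinib dose, at least 72 h after the Period 1 dabigatran dose: 72/8.4 = 8.57 half-lives, and 0.5^8.57 = 0.26% left. It is a sound reference.

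**5. Where does the 4 h sample sit?** Protocol section 3 gives a peak at 0.5 to 2.0 h and a 2 h delay with food. If the 0.5 to 2.0 h range is fasted (an assumption), the fed peak is expected at 2.5 to 4.0 h. The 4 h draw is then at the end of that window and is the coagulation sample nearest the peak. The aPTT limit in Protocol 5.5.2 is stated for the peak.

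**6. What shifts against the period baseline would add.** Per subject and parameter there are 4 shifts (4 h and 24 h in each period). With 3 parameters and 20 completers: 20 × 4 × 3 = 240. If 4 subjects leave after Period 1: 20 × 2 × 3 + 16 × 2 × 3 = 120 + 96 = 216. These figures count table entries; they do not measure an effect on any conclusion.

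**The case against.** The strongest reply is that the data are already reported. SAP 15.3 summarises every laboratory parameter by time point with the treatment shown, as absolute values and as change from baseline. It also flags out-of-range values and lists them separately. Clinically relevant abnormalities become adverse events, which are tabulated by treatment. All of this is correct, and it limits the weight of the point. Means and listings still do not give the number of subjects per treatment who shift out of range, which is what a shift table is for.

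Discharge is not defined in the SAP and could be programmed as the last inpatient value. That conflicts with footnote j of Table 2. It would also admit only the Day 9 sample, 1 of 4, with no 4 h value and no Period 1 comparator.

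Protocol 8.5.4 names no time points and does not mention coagulation, so choosing contrasts is legitimate work for the SAP. That is fair, but a contrast that yields no pairs for a group the SAP includes does not deliver shifts after dosing.

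The secondary endpoint is worded for tepotinib alone and in combination, so dabigatran-alone shifts lie outside it. They are nevertheless the comparator, and in Period 2 alone the count is still 0 of 2.

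Two qualifications stand. An Early Termination Visit soon after dosing could give an on-drug End of Trial value, so the off-drug statement applies to completers. A normal/high shift may also saturate on dabigatran alone, which is a reason to keep the continuous summaries beside it.

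**Conclusion.** The concern holds. For coagulation, 1 of the 2 named contrasts can be produced. It uses 2 of 9 scheduled samples per subject and none of the 4 post-dabigatran samples. This falls short of the shift analysis in Protocol 8.5.4, and SAP 7 does not declare the difference.

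The conclusion rests on discharge meaning Day 11, as the protocol has it, and on subjects completing the trial. It concerns shift tables only. It is a modest safety-reporting gap: data capture, the stopping rules and the primary PK analysis are untouched. The correction is worth making because it is nearly free.

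**What to change.** In SAP 15.3, for thrombin time, aPTT and Hemoclot:

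- Replace the discharge contrast with shifts from the SAP 9 period baseline to 4 h and to 24 h after dabigatran, with Period 1 Days 1–2 beside Period 2 Days 8–9. Use CTCAE grade where possible and the normal range otherwise.
- For Period 2, add shifts from the Day 8 pre-dose value as a supplement. As the only reference, it would subtract any effect of tepotinib itself.
- Keep the continuous change-from-baseline summaries.
- Keep End of Trial against Screening as an overall recovery check, not split by treatment.

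A useful extra, which the protocol does not promise, is the number of subjects per treatment with aPTT above ULN and above 3 × ULN, in the style of the QTcF categories in SAP 15.5.

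Leave the discharge contrast in place for hematology and biochemistry in Period 2, where it works.

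The cost is SAP wording and one table. Every sample is already scheduled, so there are no new blood draws.

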15.4 Vital Signs

Vital signs will be listed by subject and time-point and summarized for absolute values and changes-from-baseline by visit and treatment using descriptive statistics. Descriptive statistics tables will start at baseline.

15.5 ECG Evaluation

ECG data will be listed by subject and time-point and summarized for absolute values and changes-from-baseline by treatment group using descriptive statistics. Descriptive statistics tables will start at baseline. Clinically significant ECG findings for individual subjects will be listed and summarized.

The time intervals (PR, QRS, RR, QT and corrected QT intervals [based on Fridericia's formula, QTcF]) will be summarized descriptively by treatment.

The Fridericia's Correction (QTcF) is derived as follows:

$$\text{Fridericia's Correction (QTcF)} \quad QTc_f = \frac{QT}{\sqrt[3]{RR}}$$

where: RR = RR-interval measured in seconds.

Observed QTcF values will be categorized according to their absolute values into the categories

- ≤ 430 ms,
- > 430 and ≤ 450 ms,
- > 450 and ≤ 480 ms,
- > 480 and ≤ 500 ms, and
- > 500 ms,

and categorized according to their absolute change from baseline into the categories

- ≤ 30 ms,
- > 30 and ≤ 60 ms, and
- > 60 ms.

The number and percentage of subjects by these categories at any post-dose assessment will be tabulated by treatment group.

All ECG measurements will be listed, with abnormalities indicated.

Investigator reported interpretation results will also be listed and tabulated treatment using the number and percentage of subjects for each interpretation category (Normal, Abnormal Not Clinically Significant [NCS], Abnormal Clinically Significant [CS]).

16 Analyses of Other Endpoints

16.1 Pharmacokinetics

General Specifications for Plasma Concentration Data

PK concentration data of total dabigatran and tepotinib and its metabolites in plasma will be presented in tables and descriptively summarized by treatment and nominal time point using n, arithmetic mean, SD, SEM, median, minimum, maximum, and CV%. Values below the LLOQ will be taken as zero for descriptive statistics of PK concentrations. Descriptive statistics of PK concentration data will be calculated using values with the same precision as the source data, and rounded for reporting purposes only. The following conventions will be applied when reporting descriptive statistics of PK concentration data:

Mean, Min, Median, Max: 3 significant digits

SD, SEM: 4 significant digits

CV%: 1 decimal place

For final evaluations values greater than the upper limit of quantification (ULOQ) are not accepted and should be replaced by valid numeric values from dilution measurement. Missing concentrations (e.g. no sample, insufficient sample volume for analysis, no result or result not valid) will be reported and used generally as “N.R.”. Pre-dose samples that occur before the first drug administration will be assigned a time of 0 hours, as if the sample had been taken simultaneously with the study drug administration.

General Specifications for PK Parameter Data

PK parameter data of total dabigatran, tepotinib and its metabolites in plasma will be presented in tables and descriptively summarized by treatment using n, arithmetic mean, SD, standard error of the mean (SEM), median, minimum, maximum, CV%, GeoMean, the geometric coefficient of variation (GeoCV%), and the 95% CI for the GeoMean.

PK parameter C_{max} will be reported with the same precision as the source data. All other PK parameters will be reported to 3 significant figures. In export datasets, as well as in the SDTM PP domain, PK parameters will be provided with full precision, and will not be rounded.

Descriptive statistics of PK parameter data will be calculated using full precision values, and rounded for reporting purposes only.

The following conventions will be applied when reporting descriptive statistics of PK parameter data:

Mean, Min, Median, Max, GeoMean, 95% CI: 3 significant digits

SD, SEM: 4 significant digits

CV%, GeoCV%: 1 decimal place

Ratio of GeoMean and 95% CI 4 decimal places

To ensure a reliable estimate of the extent of exposure, AUC_{extra} should be less than or equal to 20%. If AUC_{extra} is greater than 20%, all parameters derived using λ_z (ie, λ_z , $t_{1/2}$, $AUC_{0-\infty}$, AUC_{extra} , Vz/f , CL/f) will be listed, but set to missing for the calculation of descriptive statistics.

All statistical analyses and descriptive summaries of pharmacokinetic data will be performed on the PK Analysis Set. All available concentration/PK data will be listed. Data of subjects not in the PK analysis set or invalid data will be flagged accordingly.

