**Secondary endpoints:**

- PK profile of total dabigatran (unconjugated plus conjugated) in terms of time of the maximum drug concentration ( $t_{max}$ ), terminal half-life ( $t_{1/2}$ ), percentage of  $AUC_{0-\infty}$  obtained by extrapolation ( $AUC_{extra\%}$ ), apparent total body clearance (CL/f), apparent volume of distribution during terminal phase ( $Vz/f$ ) at Day 1 of Period 1 and Day 8 of Period 2 from time zero to 72 h post-dose.
- Occurrence of TEAEs (incidence, frequency, intensity and causality), occurrence of changes in safety laboratory assessments, 12-lead ECGs and vital signs in subjects receiving tepotinib alone and together with dabigatran etexilate assessed from Day -1 of Period 1 until the End of Trial Visit.

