### **8.5.3 Analysis of Secondary Endpoints**

Summary statistics will be provided for all secondary PK parameters as well as for the concentrations of dabigatran in plasma by time point.

For  $t_{max}$  of dabigatran the Hodges-Lehmann shift estimator will be calculated together with the 90% confidence interval according to Tukey.

PK variables will be evaluated and listed for all subjects of the PK population.

Graphical displays will be given, where appropriate. Details of the statistical analysis will be described in the statistical analysis plan.

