8.2 Definition of Analysis Sets and Subgroups

For purposes of analysis, the following populations are defined:

Population	Description
Screening	The screening analysis set will include all subjects who provided signed informed consent, regardless of treatment status in the trial. This set will be used for subject disposition.
Safety	The Safety Analysis Set will include all subjects who have received at least 1 dose of planned IMP. Subjects will be analyzed according to the actual treatment they receive.
Pharmacokinetic	The PK Analysis Set will include all subjects who have completed at least 1 period without any relevant protocol violations with respect to factors likely to affect the comparability of PK results, with adequate study medication compliance, and with evaluable dabigatran PK data. Assessment of data sufficiency will be done by the responsible pharmacokineticist before database lock, ie PK data will be available and included in the database before data base lock. Subjects may be excluded after vomiting or following diarrhea in a particular period as this could render the plasma concentration-time profile unreliable. The use of a concomitant medication that might interfere with the PK of any investigational drug could be a reason for excluding a subject.

9

General Specifications for Data Analyses

Statistical analyses will be performed using the computer program package SAS® System for Windows™ (Version 9.4 or later; SAS Institute, Cary, North Carolina, USA).

The results of this trial will be reported using summary tables, figures, and data listings, as appropriate. All data will be summarized by treatment and/or scheduled time point, as appropriate.

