16.1.1 Primary Endpoints

A general linear model with TREATMENT and SUBJECT as fixed effects will be applied to log-transformed PK parameters C_{max} , AUC_{0-t} , and $AUC_{0-\infty}$ of dabigatran (measured as total dabigatran) based on the PK analysis set. Treatment differences on the log scale of dabigatran with tepotinib vs dabigatran alone will be estimated for C_{max} , AUC_{0-t} , and $AUC_{0-\infty}$ together with their 90% CIs. Point estimates and CIs will be back-transformed to the original scale.

The primary endpoints will be descriptively summarized. Scatter plots will be produced for the individual PK parameters by treatment group indicating the geometric means within each treatment group.

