16.1.2 Secondary Endpoints

Summary statistics will be provided for all secondary PK parameters by treatment.

Individual estimates of relative bioavailability of dabigatran (dabigatran with tepotinib/dabigatran alone) will be calculated for each subject and listed and summarized.

For t_{max} of dabigatran the Hodges-Lehmann shift estimator (dabigatran with tepotinib - dabigatran alone) will be calculated together with the 90% confidence interval according to Tukey.

PK variables will be evaluated for all subjects of the PK population. PK variables will be listed for all subjects with available data in the safety set.

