CL _{SS/f}	Apparent total body clearance of drug at steady state following extravascular administration, considering the fraction of dose absorbed. CL _{SS/f} = Dose p.o. / AUC _τ (parent drug only)
C _{max,SS}	Maximum observed plasma concentration during a complete dosing interval at steady state
C _{min,SS}	Minimum observed plasma concentration during a complete dosing interval at steady state
t _{max,SS}	The time to reach the maximum observed plasma concentration collected during a dosing interval (unless otherwise defined, take the 1 st occurrence in case of multiple/identical C _{max} values)
F _{rel,test/reference}	Relative bioavailability, defined as AUC _{0-∞,test} /AUC _{0-∞,reference} ,
	$F = \frac{AUC_{0-\infty, \text{test}}}{AUC_{0-\infty, \text{reference}}} * 100$

Individual PK parameters will be calculated using actual sampling times. The predose sample will be considered as if it had been taken simultaneously with the administration of study drug. PK variables will be evaluated and listed for all subjects who provide sufficient concentration-time data.

Plasma concentrations below LLOQ before the last quantifiable data point will be taken as zero for calculating the AUC (ie, embedded BLQ values set to zero). Plasma concentrations below LLOQ after the last quantifiable data point will not be considered for the determination of λ_z.

The following PK parameters will be calculated for diagnostic purposes and listed, but will not be summarized:

- The time interval (h) of the log-linear regression (λ_{z low}, λ_{z upp}) to determine λ_z.
- Number of data points included in the log-linear regression analysis to determine λ_z.
- Goodness of fit statistic (Rsq) for calculation of λ_z.

The regression analysis should contain data from at least 3 different time points in the terminal phase consistent with the assessment of a straight line on the log-transformed scale. Phoenix WinNonlin best fit methodology will be used as standard. The last quantifiable concentration should always be included in the regression analysis, while the concentration at t_{max} and any <LLOQ concentrations that occur after the last quantifiable data point should not be used.

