The coefficient of correlation (R^2) should be ≥ 0.8 and the observation period over which the regression line is estimated should be at least twofold the resulting $t_{1/2}$ itself. If these criteria are not met, then the corresponding values should be flagged in the listing displaying Individual Plasma Pharmacokinetic Diagnostic Parameters for Each Treatment. Any flags should be included in the study specific SDTM. Then the rate constants and all derived parameters (e.g. $AUC_{0-\infty}$, $\%AUC_{extra}$, CL/f , $t_{1/2}$, and Vz/f) will be included in the parameter listings and will be discussed appropriately in alignment with the protocol lead and quantitative pharmacology representative.

Partial areas AUC_{τ} should be calculated using the scheduled dosing interval, as defined in the Clinical Trial Protocol. The actual dosing interval calculated from eCRF time data should not be used. The following rules apply when calculating the partial area AUC_{τ} within the observed time interval from T_1 to T_2 :

- If the start time of the interval (T_1) occurs before the first observation, the observation at T_1 will be estimated using the linear interpolant between the first datapoint and C_0 . For single dose data $C_0 = 0$ when the drug was administered via an extravascular route. For steady state models, C_0 is the minimum concentration value occurring within the time interval T_1 to T_2 .
- If either T_1 or T_2 falls within the time range in which samples were taken, but does not coincide with an observed data point, then a linear or logarithmic interpolation is performed to estimate the corresponding concentration value. Whether a linear or logarithmic interpolation is used will depend on the method of AUC calculation e.g. linear up log down.
- If the end time of the interval (T_2) occurs after the last measurable concentration and the terminal regression (λ_z) is estimable, then λ_z is used to estimate the concentration at time T_2 . The log trapezoidal rule will be used to calculate the area from the last observation time to the end time of the partial area (T_2). If λ_z cannot be estimated the partial area will not be calculated.

The IMP dose administered is given for the monohydrate hydrochloride salt (ie, 500 mg IMP). A conversion factor for the freebase IMP was calculated and will be applied when 'dose' is used in deriving PK parameter formulas needing a dose value (CL/f).

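### The 20% extrapolation rule blanks the endpoint that triggers it, so the summary statistics for AUCextra% can never show a value above 20%

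*SAP*

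**What the plan says.** SAP section 16.1, in the specifications for PK parameter data, sets a limit of 20% on AUCextra so that the extent of exposure is reliably estimated. Above the limit, all parameters derived using lambda_z "will be listed, but set to missing for the calculation of descriptive statistics". The list given there is lambda_z, t1/2, AUC0-inf, AUCextra, Vz/f and CL/f.

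The Protocol (sections 5.1 and 8.3.2) and the SAP (section 5) name the percentage of AUC0-inf "obtained by extrapolation" as a secondary endpoint for total dabigatran in both periods. On reporting, SAP 16.1.2 states: "Summary statistics will be provided for all secondary PK parameters by treatment". Protocol 8.5.3 states: "Summary statistics will be provided for all secondary PK parameters as well as for the concentrations of dabigatran in plasma by time point". Under SAP 16.1 these statistics are n, mean, SD, SEM, median, minimum, maximum, CV%, geometric mean, geometric CV% and the 95% CI of the geometric mean.

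For other lambda_z problems (R2 below 0.8, or a regression span shorter than two half-lives), SAP 16.1.5 says "then the corresponding values should be flagged in the listing" and calls for discussion of the derived parameters.

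**The concern.** Leaving AUC0-inf, CL/f, Vz/f and t1/2 out of a summary is defensible when much of the area is extrapolated, because those values are then poorly determined. AUCextra% is different: it is the measure that tells the reader how far AUC0-inf can be trusted. Dropping its high values removes the profiles it exists to reveal. The table would look acceptable in every possible dataset, and the number of heavily extrapolated profiles would have to be worked out from a fall in n or counted from the listings.

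**Working it through.** The plan states no figure that depends on this rule, so there is nothing to reproduce. The check is a reading of the rule, then arithmetic on when it would fire.

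**1. Does the list cover the percentage?** The SAP abbreviations define AUCextra (an area) and AUCextra% separately, and the list prints the symbol without the % sign. The limit is a percentage, so it makes sense only for AUCextra%. The lead-in covers all parameters derived using lambda_z, and SAP 16.1.5 counts the percentage among the parameters derived from the rate constant. The percentage is therefore covered.

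**2. The cap.** Let X be AUCextra% in one profile. The summary uses only profiles with X ≤ 20. Its maximum is then at most 20, and so are its mean, median and geometric mean. This needs no assumption about the data.

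**3. How truncation acts.** As illustration only, take X as lognormal with median m, s² = ln(1 + CV²) and b = ln(20/m)/s. The mean of all values is m·exp(s²/2). The tabulated mean is that times Φ(b − s)/Φ(b). The medians and CVs are assumed.

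| Assumed median, CV | Share above 20% | Mean, all profiles | Mean as tabulated |
|---|---|---|---|
| 3%, 100% | 1.1% | 4.2% | 4.0% |
| 10%, 60% | 10.6% | 11.7% | 9.9% |
| 20%, 50% | 50% | 22.4% | 14.2% |

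**4. When would the rule fire?** Inputs are a terminal half-life of 8.4 h with GeoCV 12.0% (Protocol section 3) and samples at 12, 24, 36, 48 and 72 h (Protocol 7.5.1).

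- Mono-exponential decline: AUCextra% = 100 × 2^(−t_last/8.4). This gives 37.1% at 12 h, 13.8% at 24 h, 5.1% at 36 h, 1.9% at 48 h and 0.26% at 72 h. The 20% line is crossed at t_last = 8.4 × log2(5) = 19.5 h, which falls between the 12 h and 24 h samples.
- With first-order absorption: the tail is multiplied by about ka/(ka − k), with k = ln2/8.4 = 0.0825 per h. I assume tmax of 3 or 4 h; the Protocol's 0.5 to 2 h plus a 2 h food delay gives 2.5 to 4 h. Then ka = 0.866 or 0.562 per h and the factor is 1.105 or 1.172. The result is 41.1 or 43.5% at 12 h, 15.3 or 16.2% at 24 h, and 5.7 or 6.0% at 36 h.
- Longer half-lives: with t_last at 24 h, 20% is exceeded when the half-life is above 24/2.322 = 10.3 h (9.8 or 9.5 h with absorption). With s = sqrt(ln(1 + 0.12²)) = 0.1196, z = ln(10.34/8.4)/0.1196 = 1.73 and ln(9.52/8.4)/0.1196 = 1.04. About 4% to 15% of profiles would exceed 20% if all of them ended at 24 h. With t_last at 72 h the half-life would have to exceed 72/2.322 = 31 h.

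**5. What LLOQ would cause this?** The LLOQ is not stated. In the absorption model, C(24 h)/Cmax is 0.138/0.706 = 19.5% for tmax 3 h, so a typical profile ends at 12 h only if the LLOQ exceeds about a fifth of Cmax. The Protocol describes a bi-exponential decline, which lowers that threshold. A simulation with an assumed 2 h distribution half-life and 60 to 80% of AUC in the terminal phase blanked no reference profile at an LLOQ of 2% of Cmax, 0.1 to 1.8% at 5%, and 5 to 49% at 10%. That spread shows that the frequency cannot be predicted from the documents.

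**The case against.** The best defence has three parts. First, the values are not suppressed: the sentence that blanks them also says they are listed, SAP 16.1.2 lists PK variables for all safety-set subjects with data, and n is tabulated. A reader might infer that an AUCextra% above 20% can never be reported at all. The documents do not support that; only the summary is capped. A lower n, however, does not say why a profile is missing.

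Second, summary statistics for every secondary parameter will be produced, and section 16.1 only specifies how. It would go too far to call this a broken commitment. What stands is that the specified summary is truncated on its own value.

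Third, values above 20% come from short profiles and are imprecise, and the rule may never fire. Both are fair and keep the point minor. Imprecision calls for a flag, and a summary rule should be sound before the data arrive.

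Two further inferences should be resisted. The flagging rule in SAP 16.1.5 does not say that flagged values stay in the descriptive statistics, so it is no precedent for summarising them. Nor does the rule reach the primary analysis: SAP 16.1.1 says "A general linear model with TREATMENT and SUBJECT as fixed effects will be applied to log-transformed PK parameters" Cmax, AUC0-t and AUC0-inf, while the blanking is limited to descriptive statistics. The plain reading is that the model keeps AUC0-inf values above 20%, although the SAP does not say so expressly. Whether relative bioavailability falls under the rule is also unstated, but that is missing detail and not part of this point.

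**Conclusion.** The point holds as a minor defect. As written, the rule cuts the summary of a named secondary endpoint off at 20%, and the summary understates extrapolation in any dataset where the rule fires. The cap follows from the text once AUCextra is read as the percentage, which the 20% limit and SAP 16.1.5 support. The practical size is unknown without the LLOQ. It is nil if profiles stay quantifiable to 36 h or beyond with half-lives near 8.4 h. It becomes material if many profiles end at 12 h, or if they end at 24 h in subjects with half-lives above roughly 9.5 to 10.3 h. Protocol 5.2.3 expects measurable profiles at the 75 mg dose, so few cases are likely. No estimate, confidence interval or power figure for the primary endpoints changes.

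**What to change.** In SAP 16.1, remove AUCextra and AUCextra% from the parameters set to missing and leave the rule as it is for the others. Suggested addition: AUCextra% will be summarised by treatment for all profiles in the PK Analysis Set with an estimable lambda_z; the number and percentage of profiles above 20% will be given by treatment, and these values will be flagged.

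The cost is one deleted list item, one table row and a flag. It needs no new data and leaves the primary model and power untouched. The drawback is that the summary will contain some imprecise values from short profiles, which is why the flag is needed.
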